#### 3.12 Study reporting

The study will be reported according to the principles of the CONSORT Statement.

#### 3.13 Recording of adverse or serious adverse events

Adverse events, or serious adverse events, are all (serious) adverse changes from the baseline of the participant which are deemed clinically relevant by the respective clinical doctor, including:

- Occurrence of a new clinically significant disorder
- Worsening or increased frequency and/or intensity of pre-existing medical conditions
- clinically significant laboratory results outside of reference standards

These changes may not be necessarily directly related to the study intervention but will be recorded in the eCRF by the respective study doctor. Adverse or serious adverse events do not include:

- Planned interventions or hospitalisations
- Planned medical or surgical treatment, including surgeries, endoscopic examinations, tooth extractions, or blood transfusions

• Underlying medical conditions (except for those mentioned in the exclusion criteria) which do not worsen throughout the course of the study

No adverse or serious adverse events are expected in TirolGESUND as the interventions are based solely on health-promoting lifestyle changes.

# 4 Study population

#### 4.1 Eligibility

#### 4.1.1 Inclusion criteria

- 1. Women aged 30 to 60
- 2. Motivated to change their lifestyle
- 3. Smoking cessation:  $\geq 10$  cigarettes per day for at least the last five years
- 4. Dietary intervention: BMI between 25 and 35
- \* Should 3 and 4 apply, the participant will be allocated to the smoking cessation group.

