#### 4.1.2 Exclusion criteria

- 1. Relevant underlying conditions
  - (a) Current or previous malignant tumour or cancer
  - (b) Current or previous significant cardiovascular disorder Women with elevated blood pressure are allowed to participate as long as it is well controlled under their current medication
  - (c) Current or previous metabolic disorder (e.g., diabetes type I or II) In the dietary intervention arm, participants with current hypothyroidism/Morbus Hashimoto will be excluded as the switch to intermittent fasting may require a adjustment of their medication
  - (d) Current or previous psychiatric disorder (e.g., eating disorder, depression)
- 2. Current pregnancy or lactation period
- 3. Total hysterectomy
- 4. Known current or previous premalignant lesion of the cervix uteri (CIN2/3)
- 5. Concurrent participation in another interventional trial

Participants for which inclusion criteria 1b, c, d, 2, 3, and 5 occur after inclusion in the study will be excluded from the study.

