# 5.4 Definition of primary, secondary, and subsidiary endpoints

#### 5.4.1 Primary objective

To assess whether a reduction/cessation in risk exposure (smoking, continuous non-timerestricted calorie intake resulting in being overweight/obese) via lifestyle modification over six months results in significant absolute changes in DNA methylation-based disease risk and ageing scores compared to baseline in cervical samples. Scores of the following age signatures will be evaluated:

- signatures that have previously been published, including
  - WID-BC
  - WID-OC
  - WID-EC
  - WID-CIN
  - WID-REA
  - WID-RIA
  - pcgtAge
- signatures that are not yet published but have been developed by the study group
  - Group of markers indicative of (stem) cellular age, e.g. WID-PCGT (general/immune/epithelial),
    WID-SEN (general/immune/epithelial), WID-PRO (general/immune/epithelial),
    etc. thereafter referred to collectively as "WID-SOLA"
- signatures indicative of exposure, e.g.
  - WID-SMK smoking index

Successful completion relates to a significant reduction in two ore more risk scores with no significant in increase in any of the scores.

Analysis will be conducted both ITT, intention to treat, and PP, per protocol, comparing baseline and month 6. ITT analysis may be conducted as a mixed-effects models, using compliance score as a covariate. A per protocol analysis may be conducted either by median compliance rate above or equal to 80%, or alternative split by mean or median compliance rate (see Figure 1).

Subgroup analyses will also be conducted as follows:

- 1. smoking cessation study arm: investigation of the impact of the use of electronic cigarettes on smoking signature scores
- 2. intermittent fasting study arm: investigation of difference between individuals who received ketogenic supplement and those that did not at 6 months
- 3. intermittent fasting study arm: subgroup analysis by fasting pattern (breakfast or dinner skipping)

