#### Clinical and epidemiological endpoints

- body mass index (BMI), diet arm of the study
- body composition (muscle, fat, water), diet arm of the study
- smoking status, *smoking arm of the study*, including

- current smoking (yes/no)

- cigarettes in the last 7 days
- use of nicotine replacement products
- vascular health

pulse wave velocity, intima-media thickness, and plaque score before and after intervention

- abdominal fat composition, *diet arm of the study* visceral and subcutaneous fat before and after 6 months of intervention
- physical activity and health measured using the international physical activity questionnaire (IPAQ), sports examination (VO2max), and fitness tracker (daily steps, active minutes, floors climbed); resting heart rate
- pulmonary health

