# 6.6 Microbiome data

The following questions will be addressed:

1. How do intermittent fasting or smoking cessation influence the gut microbiome? Is there a shift in dominant types? Is there an increase in species richness? Is there an increase in the relative abundance of genera associate with a healthy phenotype, or loss of species associated with a disease phenotype?

A comparison will be conducted between month 0 and month 6. Data will be analysed in association with the compliance score, as well as epigenetic markers and BMI. Beneficial species include probiotic and short-chain fatty acid producing microbes:

- *Lactobacillus reuteri*, which produces reuterin, a protein oxidant that helps to protect against colorectal cancer.
- *Parabacteroides distasonis*, which can increase levels of unconjugated bile acids that activate GLP1 and UCP1 pathways and improve the glucose and energy metabolism.
- Akkermansia muciniphilia, which induces mucin production necessary for intestinal integrity. This can also be associated with blood markers of LBP, an indicator of gut integrity.

Conversely, harmful microbiobes include species such as *Clostridium difficile*.

- Can the microbiome be used to distinguish lean from overweight or obese individuals, using fecal microbial taxonomic composition? Taxonomic composition of individuals with BMI below and above 25 will be analysed at month 0. The potential species contributing to difference may be analysed using PCA and correlation analysis.
- 3. Can the microbiome be used to distinguish smokers from non-smokers? Taxonomic composition of smokers and non-smokers will be analysed, with the caveat that non-smokers are all of BMI above 25 which may have an impact on microbiome (see above).
- 4. Are the changes in the microbiome associated with predicted functional alterations?

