# 8 Publication outline

For each sub-study (smoking cessation and intermittent fasting), one main paper will be prepared describing the overall effects on a variety of organ systems. Key aspects to epigenetic and clinical effects will be presented in the main data, while additional outcomes may be presented in supplementary data, although this will need to be confirmed.

For each study, a participant flowchart diagram as well as overview for compliance will be shown. The following characteristics will be described for all participants at the beginning (and at the end) of the study, separately for each intervention:

- age
- ethnicity
- highest education
- menopausal status
- parity
- use of menopausal hormone replacement therapy (postmenopausal only)
- use of oral contraceptives
- body mass index  $(kg/m^2)$
- body composition from bioelectric impedance analysis (% mass), diet group only
- abdominal fat (visceral and subcutaneous, both in mm)
- resting heart rate
- smoking status (current/ex/never smoker)
- smoking pack year

Data will be reported in a table, describing the parameters using mean or median and standard deviation or quantiles, respectively, or proportions (%) depending on data type and distribution.

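### The diet sub-study can enrol current smokers below the smoking-arm threshold, so a fall in WID-SMK caused by reduced smoking could be read as an effect of fasting

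*SAP*

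**What the plan says.** **Eligibility.** SAP 4.1.1 sets the smoking-arm threshold at 10 or more "cigarettes per day for at least the last five years". The diet criterion is "Dietary intervention: BMI between 25 and 35", with no smoking condition. The overlap note reads "Should 3 and 4 apply, the participant will be allocated to the smoking cessation group". The exclusion list in 4.1.2, which ends with "Concurrent participation in another interventional trial", does not mention smoking.

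**Primary analysis.** SAP 5.4.1 lists "WID-SMK smoking index" as an exposure signature in the primary set, without limiting it to one sub-study. Section 6.4.3 tests baseline against month 6 by paired Wilcoxon on scores adjusted for immune cell composition. Sections 3.1 and 5.3 confirm that there is no control group, apart from a possible nested group of non-adherent women. Success needs a significant reduction in at least two risk scores and no significant increase in any score.

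**Smoking data.** The endpoint list in 5.4.2 has "smoking status, *smoking arm of the study", and section 3.4 places cotinine and seven-day cigarette counts under smoking cessation. Section 6.5.3 lists current smoking with no arm label. Section 8 lists "smoking status (current/ex/never smoker") for all participants at the beginning (and at the end), separately for each intervention.

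**The concern.** The two entry routes do not separate smokers from non-smokers. They separate women who meet the whole smoking criterion from women who do not. A woman with BMI 28 who smokes 8 cigarettes a day for 20 years, or 20 a day for four years, fails the smoking criterion, meets the diet criterion and is excluded by nothing in 4.1.2.

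A change in smoking among such women is plausible. Inclusion requires motivation to change lifestyle, and section 3.3 gives every participant weekly personal coaching. A woman who smokes less at month 6 than at month 0 would be expected to show lower WID-SMK, and possibly lower values of other smoking-sensitive scores. With baseline as the only comparator and no smoking term in the primary test, that fall cannot be told apart from an effect of fasting. What is at stake is the interpretation of one primary-set score in the diet sub-study, and possibly its contribution to the success rule.

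**Working it through.** The SAP gives no number of diet-arm smokers and no expected WID-SMK change, so there is no plan figure to reproduce on this point. The sample-size statement in 3.6 is not affected: Φ(0.2 × √60 / 0.44 − 1.96) = 0.941, which agrees with the stated power of 0.94.

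**Inputs.** From the SAP: 120 women in the diet sub-study. Assumed: a share f of them smoke at month 0 (10% = 12 women; 20% = 24 women), and a share q of those cut down or quit (25% to 50%). All 120 are taken to have both samples.

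**Step 1, mean change.** Bias in the mean WID-SMK change = f × q × (change on quitting).
- q = 0 (stable smoking): 0.
- f = 10%, q = 25%: 0.10 × 0.25 = 2.5% of the quitting effect.
- f = 20%, q = 50%: 0.20 × 0.50 = 10% of the quitting effect.

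**Step 2, the planned Wilcoxon test.** Suppose there is no true fasting effect and the k women who change smoking have the k largest falls, which is the worst case for rank position.
- SD of the signed-rank sum for n = 120: √(120 × 121 × 241 / 24) = √145,805 = 381.8.
- k = 3 (10% × 25%): ranks 118 to 120 sum to 357. Half of that, 178.5, is the shift from expectation. Expected z = −178.5 / 381.8 = −0.47.
- k = 12 (20% × 50%): ranks 109 to 120 sum to 1,374; half is 687. Expected z = −687 / 381.8 = −1.80.

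The chance of a falsely significant reduction at two-sided 0.05 is nominally 2.5%. For k = 3 it becomes Φ(−1.96 + 0.47) ≈ 7%. For k = 12 it becomes Φ(−1.96 + 1.80) ≈ 44%. Both use the null SD; allowing for the fixed signs of the k women gives about 6% and 43%.

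**Step 3, microbiome question 3 (section 6.6).** If women were classed by arm, and diet-arm smokers carried a fraction r of the full smoker effect, the observed contrast would be (1 − f × r) of the true one. For r from 0.25 to 1 that is 0.975 to 0.90 at f = 10%, and 0.95 to 0.80 at f = 20%. If women are classed by recorded status, there is no attenuation.

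**The case against.** The strongest reply is that the SAP already has what it needs. Smoking status is listed for all participants in section 8. Section 6.4.2 plots month 0 scores against it. Section 6.4.4 names it as a possible covariate and calls its models examples whose covariates may change, so its absence from the example fasting model is not a fixed omission. All of this stands. A reader might infer from the arm label in 5.4.2 that smoking is tracked only in the smoking arm; section 8 rules that out. What section 3.4 confines to smoking cessation is cotinine and cigarette counts.

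A reader might also infer from the remark in 6.6 that the "non-smokers are all of BMI above 25" that the whole diet arm is treated as non-smokers. The text does not say so. The remark is true even if some diet-arm women smoke, because non-smokers can enter only through the BMI criterion. The attenuation in Step 3 therefore depends on a classification rule that the SAP never states.

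Third, the primary test is within person, so only women who change matter, and WID-SMK alone cannot deliver success because at least two risk scores must fall. Fourth, coaching and exercise go to everyone and the study is declared exploratory, so attribution to fasting is limited anyway. Both are fair and lower the weight of the point. They do not remove it: none of the planned covariate provisions is mandatory, the primary test carries no smoking term, and smoking is the exposure that WID-SMK is meant to measure.

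**Conclusion.** The point holds as a moderate gap in the diet sub-study's primary analysis. Eligibility admits current smokers below either part of the threshold, and a reduction in their smoking would appear as a WID-SMK fall after fasting. The size rests on assumed shares. With 3 changers of 120 the test is barely disturbed (z about −0.5). With 12, the risk of a false reduction is serious (z about −1.8), but this needs 20% smokers, half of them changing, and all of them holding the largest falls. It would go too far to say that smokers supply much of any WID-SMK reduction; the documents give nothing to show it. The definition of non-smoker in microbiome question 3 and the arm label in 5.4.2 are points of clarification only.

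**What to change.** Add to SAP 6.4.3, for the diet sub-study: repeat the primary paired analysis without women who smoked at month 0. State that a WID-SMK fall is not attributed to fasting, and does not count towards success, unless it also holds in that set. Leaving these women out is safer than adjusting for a change in status, because the current/ex/never item does not show cutting down.

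As clarifications: in 6.6, define smokers and non-smokers for question 3 by recorded month 0 status; and reconcile the smoking-arm label in 5.4.2 with the unlabelled item in 6.5.3 and the all-participant list in section 8.

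The cost is a few sentences and one sensitivity analysis on data already planned. The downside is a somewhat smaller set: 120 − 12 = 108 or 120 − 24 = 96 women under the assumed shares, before dropout. Eligibility need not change.

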#### 4.1.2 Exclusion criteria

- 1. Relevant underlying conditions
  - (a) Current or previous malignant tumour or cancer
  - (b) Current or previous significant cardiovascular disorder Women with elevated blood pressure are allowed to participate as long as it is well controlled under their current medication
  - (c) Current or previous metabolic disorder (e.g., diabetes type I or II) In the dietary intervention arm, participants with current hypothyroidism/Morbus Hashimoto will be excluded as the switch to intermittent fasting may require a adjustment of their medication
  - (d) Current or previous psychiatric disorder (e.g., eating disorder, depression)
- 2. Current pregnancy or lactation period
- 3. Total hysterectomy
- 4. Known current or previous premalignant lesion of the cervix uteri (CIN2/3)
- 5. Concurrent participation in another interventional trial

Participants for which inclusion criteria 1b, c, d, 2, 3, and 5 occur after inclusion in the study will be excluded from the study.

# 4.2 Recruitment

Participants will be recruited via Tirol Kliniken, University of Innsbruck, other larger employers in Tirol (e.g. Bäcker Ruetz), via staff emails/intranet, online videos, posters, and employee magazines, or via personal recommendation from participating study investigators.

# 5 Statistical principles

# 5.1 Significance levels and adjustment of p-values for multiplicity

Significance levels throughout are set at p < 0.05. Formal adjustment for primary and secondary outcomes may be conducted using Benjamini-Hochberg or Bonferroni correction as appropriate, although formal adjustments may not be strictly necessary for outcomes of more exploratory or descriptive nature, as previously argued. For subsidiary outcomes, no formal correction will be applied. 95% confidence intervals will be presented for estimates of effects throughout.

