# 6.13 Subsidiary analysis: epigenetic signatures of reprogramming

We will investigate whether DNAme regions or individual CpGs that change after Yamanaka factor reprogramming (OSKM) in blood cells (PBMCs) at month 0 also change during the intervention, in both smoking cessation and intermittent fasting.

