## 6.13.2 Subsidiary endpoint reporting

We will investigate epigenetic changes before and after reprogramming in samples collected at baseline. The same regions identified here will be investigated in the same individuals at month 6, e.g. paired t-test mean or median methylation in significant CpGs before and after reprogramming and before and after intervention). For regions that change across participants, these can be investigated after intervention even in those individuals for whom no reprogramming analysis was conducted

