# 6.14 Subsidiary analysis: meaningful biomarkers of intervention

Many studies have previously identified signatures that that capture epigenetic ageing yet the biological meaning of them remains unclear. It may be beneficial to identify CpG markers that are changed in response to a putative health-promoting intervention specifically and correlate with clinically meaningful changes (e.g. gut microbiome, lung function) in a well-characterised longitudinal dataset. We may chose to undertake this subsidiary analysis pending the outcome of initial results. This analysis is largely explorative and may depend on the data. DNA methylation features associated with the intervention and changes in other biologically meaningful changes (e.g. microbiome, lung function) may be identified. Scores can be investigated in a hold-out test set and ongoing follow-on projects at our institute (SUN and LIFE Tirol), which investigate smoking cessation in n=200 participants and randomised intermittent fasting in approximately n=800 participants.

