# 7 Systems medicine approach

In addition to the above, we also intend to assess which of the WID scores that dynamically change as a function of protocol adherence are correlating with the change of any of the nonmethylation parameters, for example association of microbiome markers in with epigenetic age (WID-SOLA markers).

Briefly, we aim to conduct three analyses:

- 1. Evaluation of dynamics of prespecified epigenetic markers (WID scores) within the three surrogate tissues cervix, blood, and buccal, in order to assess whether changes are concordant or discordant, both directional and temporal (part of secondary outcome analyses)
- 2. Investigation of prespecified epigenetic markers and their correlation to non-methylation parameters, for instance whether microbiome or lung function markers are associated with any cellular/immune ageing markers (WID-RIA/WID-SOLA)
- 3. Agnostic approach, where non-methylation parameters are the outcome and predictors are defined based on DNAme to identify whether CpG sites which predict the nonmethylation features (part of subsidiary exploration).

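### The SAP exempts every subsidiary outcome from multiplicity correction, including CpG-level discovery on the methylation array, so CpG lists called at p < 0.05 would have no control of false discoveries

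*SAP*

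**What the plan says.** Section 5.1 sets one threshold for the whole plan: "Significance levels throughout are set at p < 0.05". It then treats the tiers differently. For the upper two tiers correction is optional: "Formal adjustment for primary and secondary outcomes may be conducted using Benjamini-Hochberg or Bonferroni correction as appropriate". For the third tier the rule is flat: "For subsidiary outcomes, no formal correction will be applied". High-dimensional analyses are not excepted.

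Three subsidiary analyses look for CpGs:

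- **Reprogramming (6.13, 6.13.2).** "We will investigate whether DNAme regions or individual CpGs that change after Yamanaka factor reprogramming" in baseline blood cells also change during the intervention. The example test is a "paired t-test mean or median methylation in significant CpGs before and after reprogramming", and likewise before and after the intervention.
- **Intervention biomarkers (5.4.3, 6.14).** "It may be beneficial to identify CpG markers that are changed in response to a putative health-promoting intervention specifically" and that also correlate with clinically meaningful change, such as gut microbiome or lung function.
- **Systems medicine (section 7, item 3).** "Agnostic approach, where non-methylation parameters are the outcome and predictors are defined based on DNAme". The plan files this under subsidiary exploration.

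Section 6.4.1 names the Illumina EPIC array as the platform. No section gives the number of CpGs to be tested, a false discovery rate, a genome-wide threshold or an effect-size filter for these analyses. Section 6.14 is described as optional and mainly exploratory. It allows, but does not require, scores to be examined in a hold-out set and in two follow-on projects of 200 and about 800 participants.

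**The concern.** Unadjusted p-values are defensible for a short list of exploratory outcomes. A screen over many thousands of CpGs is different, because the number of chance hits grows in proportion to the number of sites tested. Here a stated rule, not a missing detail, removes correction from such screens. Section 1 says the reported papers will follow this strategy, so the rule governs what is published.

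At stake are the list of CpGs reported as responding to the intervention, any score built from it, and the set of CpGs carried from reprogramming into the month 6 comparison. Section 6.14 aims to find CpG markers with biological meaning. Without control of false discoveries, a reader could not tell what part of such a list is likely to be real.

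**Working it through.** **The plan's own figure.** The only power figure is in section 3.6: n = 60, difference 0.2, SD 0.44, α = 0.05, power 0.94. Taking 0.44 as the SD of the within-person change, power = Φ(0.2 × √60 / 0.44 − 1.96) = Φ(3.52 − 1.96) = Φ(1.56) = 0.94. It reproduces, but it concerns index scores and says nothing about CpG screens.

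**Inputs.** α = 0.05 and no correction are from section 5.1. Three inputs are assumptions because the SAP does not give them: the number of CpGs m (100,000 to 900,000), the share π that truly changes (0.1% to 50%) and the power per CpG (80%).

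**Chance hits if no CpG changes.** Expected number = 0.05 × m: 5,000 at m = 100,000 and 45,000 at m = 900,000. Correlation between CpGs leaves this expectation unchanged but makes the count more variable.

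**False share among hits, one criterion.** Share = 0.05(1 − π) / [0.05(1 − π) + 0.8π]. It does not depend on m.

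| π | Calculation | False share |
|---|---|---|
| 0.1% | 0.04995 / (0.04995 + 0.0008) | 98% |
| 1% | 0.0495 / (0.0495 + 0.008) | 86% |
| 5% | 0.0475 / (0.0475 + 0.04) | 54% |
| 10% | 0.045 / (0.045 + 0.08) | 36% |
| 50% | 0.025 / (0.025 + 0.4) | 6% |

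For a false share of 90% or more, π must be at most about 0.7% at 80% power (about 1.1% at 50% power, 0.6% at 94%).

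**False share with the second criterion of 6.14.** Suppose a CpG must also correlate with one clinical feature at p < 0.05, that the two tests are independent, that each has 80% power, and that every truly changing CpG also truly correlates. The null pass rate is 0.05² = 0.0025 and the joint power is 0.8² = 0.64. Chance hits fall to 250 (m = 100,000) or 2,250 (m = 900,000).

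- π = 0.1%: 0.0024975 / (0.0024975 + 0.00064) = 80%.
- π = 1%: 0.002475 / (0.002475 + 0.0064) = 28%.

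If k independent features are scanned and any one suffices, the null pass rate becomes 0.05 × (1 − 0.95^k). This climbs back towards 0.05 as k grows, so much of the protection is lost.

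**Effect of the remedy.** Simulation with m = 100,000 independent CpGs, n = 60, standardised effect 0.2 / 0.44 = 0.4545 (power about 0.93 per CpG), 30 runs:

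| π | Hits at p < 0.05 | False share | Hits, Benjamini-Hochberg 5% | False share |
|---|---|---|---|---|
| 0 | about 5,000 | 100% | 0 | none |
| 0.1% | about 5,090 | 98% | about 10 | 4% |
| 1% | about 5,880 | 84% | about 350 | 5% |
| 10% | about 13,830 | 32% | about 7,180 | 4% |

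Bonferroni at n = 60 would leave about 3% power for that effect at m = 100,000, and 1% at m = 850,000. False discovery rate control is therefore the workable choice.

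**Reprogramming.** Section 2.2.3 looks for altered sites within each individual, but the SAP states no per-CpG test for this. The m × 0.05 count therefore cannot be applied directly. The example month 6 test averages over the selected set, so falsely selected CpGs would mainly dilute it. The gap is that nothing defines when a CpG counts as significant, and the only default is uncorrected p < 0.05.

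**The case against.** The strongest reply is that this is third-tier work. Section 6.14 is optional and called exploratory, and a hold-out set and follow-on cohorts are named. Its two-part criterion is tighter than a single screen, and no confirmatory claim rests on the lists. In 6.13 the example test is an aggregate, and results extend to other participants only for regions that change across participants. Section 7 item 3 overlaps 6.14 and speaks of predictors, which need not mean one test per CpG.

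Most of this stands as a limit on size. It does not remove the defect. The validation step is permissive, concerns scores rather than CpG lists, and is not stated for 6.13 or section 7. An exploratory label does not tell a reader which CpGs to believe. It is a reason to prefer a false discovery rate to Bonferroni.

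A reader might infer four stronger things that the SAP does not support:

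- *Almost all reported CpGs would be false.* That requires a share of truly changing CpGs below roughly 1%. The SAP gives no share, and nothing in it indicates that reprogramming alters so few sites.
- *Correction is strictest where the test family is smallest.* Correction in the upper tiers is only optional, and the secondary tier itself holds over 100 metabolites, microbial taxa and scores in three tissues.
- *The single-cell analysis is an uncorrected gene screen.* Section 6.12.3 reports cell proportions and projections, and plans no gene or peak screen.
- *The month 6 reprogramming test would produce false positives at each CpG.* The example given is an aggregate. Section 2.2.3 does ask about altered sites, but no site-level test is defined.

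**Conclusion.** The point holds in a limited form. The blanket exemption in 5.1, combined with p < 0.05 throughout, covers CpG-level discovery, and no other section supplies a threshold. Followed as written, it gives CpG lists of unknown and possibly poor reliability.

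The size is conditional. Over the assumed range the false share runs from about 6% to 98% for one criterion. With one independent clinical correlation added it is about 28% to 80% when 0.1% to 1% truly change. The count of chance hits depends on the assumed number of CpGs; the false share does not. The figures also assume 80% power per test, and do not carry over directly to the within-person selection in 6.13. The primary and secondary analyses are untouched. The change is worth making before the CpG analyses are run.

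**What to change.** In section 5.1, limit the exemption to subsidiary outcomes that are not feature screens, and add:

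> *For subsidiary analyses that test individual CpGs or regions (6.13, 6.14, section 7 item 3), significance means a Benjamini-Hochberg false discovery rate below 0.05 over all features tested in that comparison; other subsidiary outcomes are reported unadjusted and labelled exploratory.*

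In 6.13.2, define significant CpGs by the same rule, applied to a stated per-CpG test. Where 6.14 scans several clinical features, say what counts as one comparison.

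The method is already named in 5.1, so for a CpG screen the cost is SAP wording and a small code change. For 6.13 it also requires specifying the per-CpG test, which the plan lacks. The downside is a shorter list, possibly an empty one in small subgroups.
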